8.3.3. Withdrawal Criteria

Subjects will be discontinued from the study prematurely if:

1. The subject requests to be withdrawn from the study;
2. A need for a concomitant medication prohibited by the protocol arises;
3. The Principal Investigator decides that it is in the subject's best interest;
4. The subject is incompliant with the protocol;
5. The subject experiences an adverse event that requires premature withdrawal.

8.4. Randomization and Blinding

When the subjects meet admission criteria and provide written informed consent, they will receive a subject number and be randomized by subject number into one of two treatment arms. They will receive either tranexamic acid or normal saline according to the randomization schedule. The randomization schedule will be generated prior to study initiation by a statistical programmer. The pharmacy will perform and document the randomization.

Subjects will be treated according to a randomization schedule prepared prior to the start of the study. The investigator site personnel as well as Exela personnel involved in the monitoring or conducting of the trial will be blinded to the trial drug codes (or kit codes), except in the case of an emergency. Trial drug codes will not be available to the above personnel until after the completion of the trial and final data review.

An individual decoding unit containing emergency identification of the kit contents will be provided for each kit.

- i. This decoding unit must not be opened unless an actual emergency occurs. The investigator should also make a careful note of the date, time of opening, and the reason.
- ii. In the event that a decoding unit is opened, the Exela monitor must be notified immediately by the investigator.
- iii. At the conclusion of the trial, all decoding units are to be returned to Exela together with unused drug supplies.

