Study Procedures:	
Subjects who meet admission criteria will be assigned sequential numbers beginning with site#-001. A completed subject is a subject who satisfies the admission criteria and who completes all required assessments. When the subjects meet admission criteria and provide written informed consent, they will receive a subject number and be randomized by subject number into one of two treatment arms. They will receive either tranexamic acid or normal saline according to the randomization schedule.
 
Preoperative Visit: Subjects will provide written informed consent and will then undergo pre-operative data collection/screening, including:
 
• Inclusion Exclusion criteria assessment• Diagnosis leading to surgery• Planned procedure

- Schwab Curve type and coronal curve magnitude (Cobb angle)
- Patient age and demography
- Height, Weight, and Body Mass Index
- Number of units of autologous blood donation
- CBC: Hb/Hct/WBC/platelet count (post-autologous donation)
- Coagulation Profile: PT/PTT/INR
- Medical History and Medication Use
- History of Previous Spine Surgery
- Drug / Alcohol / Tobacco Use
- Medication Allergies
- Pregnancy testing (females only)

Surgery, Drug Dosing, and Hospital Stay: Blinded treatments will be administered at an initial dose of 3 mL/kg as a 1-hour infusion using a calibrated infusion pump prior to start of procedure, and as a 0.3 mL/kg/h infusion throughout the surgery. Blood lost during surgery will be collected by subfascial Hemovac drains at the incision site into canisters containing heparinized saline. Volumes collected will be recorded post-surgery and every 24 h thereafter until discharge. Measured Blood Loss will be estimated as 3 times cell saver; estimates will be taken off of the anesthesia record.

The site will provide a person who will collect blood during consult in OR and record variables and measurements on the data collection sheet throughout the entire surgery. Final Measured Blood Loss will be determined post removal of the two subfascial hemovac drains placed during the procedure.

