5. SCHEMATIC OF STUDY DESIGN

CP-006-2017 – Efficacy and safety of tranexamic acid in spinal fusion surgery

- ❖ Study Cohort - > Adult patients over age 18 electively undergoing complex spinal fusion surgery (T2 to pelvis/Sacrum, greater than 4 FSU's (5 vertebral segments or more)).
- ❖ Arm 1 - > Subjects receiving study drug (treat) (n = 100).
- ❖ Arm 2 - > Subjects receiving placebo (control) (n = 50).
- ❖ Sample size - > 150 study subjects; randomized 2:1 Treat / Control
- ❖ Intervention: Arm1 – Surgery plus study drug
Arm 2 – Surgery with placebo

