11.2. Sample Size Determination

Assuming a two-sided alpha level of 0.05, 80% power and estimated mean blood loss of 2000 mL in the control group (with a relatively low estimated standard deviation of 1000 mL due to limitations in the type of surgery and the patient population) a 25% decrease in blood loss in the treated group would require 128 patients (64 per group). Thus, the proposed sample size of 150 patients (100 active and 50 placebo) will allow 14.7% loss to follow-up which should be sufficient considering the relatively small likelihood of loss to follow-up in these patients.

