11.4.2. Analysis of Primary Efficacy Endpoint(s)

The primary efficacy variable will be total blood loss as described in Section 10.1. Since blood loss will be measured up to 24 hours after surgery and over the entire period of hospitalization, the primary measure will be the 24-hour level. Blood loss at later time-points will only be considered significant if the 24-hour measure has also reached statistical significance. Due to the hierarchical structure of this analysis, no adjustment for multiplicity will be performed.

The primary efficacy variables and continuous secondary efficacy variables will be analysed using Analysis of Covariance (ANCOVA) where one factor is treatment (TXA vs Placebo) and the other factor is Surgeon. The initial analysis will include the interaction between the

two factors in order to assess the similarity of effects across surgeons. Significant interaction effects will occur if (for example), TXA works for some surgeons but not for others. The final efficacy analysis will remove the interaction term and control for overall differences between surgeons.

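### The final model adjusts for surgeon, but the randomisation section provides no stratification or blocking by surgeon or site; depending on the number of surgeons and the structure of the list, this can cost precision that 2:1 blocks within surgeon would largely keep

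*Combined protocol and SAP*

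**What the plan says.** Section 8.4 (Randomization and Blinding) describes a schedule prepared before the study. Subjects who qualify and consent are handled as follows: "they will receive a subject number and be randomized by subject number into one of two treatment arms". The section gives no stratification factor, no block size and no statement of separate lists by surgeon or site. The schematic in section 5 gives the overall ratio: "150 study subjects; randomized 2:1 Treat / Control".

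The synopsis (Study Procedures) says that subjects are "assigned sequential numbers beginning with site#-001". That numbering is compatible with one list per site but does not establish it.

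Section 11.4.2, and the Statistical Methods entry of the synopsis, analyse blood loss by ANCOVA with treatment and surgeon as factors. The treatment-by-surgeon interaction is examined first, and then: "The final efficacy analysis will remove the interaction term and control for overall differences between surgeons".

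The sample size calculation in section 11.2 does not mention surgeon. It uses a "relatively low estimated standard deviation of 1000 mL" without saying whether this is the total SD or the SD within surgeon. The synopsis lists 8 sites. The number of operating surgeons is not stated, although Site 6 is listed with more than one investigator.

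**The concern.** With surgeon as a fixed factor, the treatment effect is estimated from comparisons within surgeons. A surgeon contributes full information only when the arms are near the planned 2:1 among that surgeon's own patients. One whose patients all fall in one arm contributes nothing. A list that ignores surgeon leaves this balance to chance.

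The plan already treats surgeon as important enough to test for interaction and to keep in the final model, so an allocation scheme that takes no account of surgeon spends precision without gain. At stake is the precision of the primary comparison, and, if surgeons are many and small, the surgeon-by-treatment assessment and any surgeon-adjusted analysis of binary endpoints. The validity of the estimate is not at stake.

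**Working it through.** **Inputs.** From section 11.2: two-sided alpha 0.05, target power 80%, control mean 2000 mL, 25% reduction (500 mL), SD 1000 mL, so a standardised effect of 500/1000 = 0.5; 150 patients as 100 active and 50 placebo. From the synopsis: 8 sites. Assumed, because the documents do not say: S = 8 to 24 surgeons, surgeon as a fixed effect, no losses, and 1000 mL as the residual SD except in step 5.

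**1. The plan's own figure.** For a active and b placebo patients, information is ab/(a+b). Power comes from the noncentral t with noncentrality 0.5 × √information. For 64 per group: 64 × 64/128 = 32; 0.5 × √32 = 2.83; 126 df; power 80.1% (63 per group gives 79.5%). The stated 128 is reproduced.

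**2. The allocation used, without surgeon.** 100 × 50/150 = 33.33; 0.5 × √33.33 = 2.89; 148 df; power 81.8%. At 2:1, 80% needs 144 patients (96 × 48/144 = 32; power 80.2%), so 150 leaves a margin of 6.

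**3. Adding surgeon.** Information becomes the sum over surgeons of a_s(n_s − a_s)/n_s, where a_s of surgeon s's n_s patients are on active drug. If the list ignores surgeon and 100:50 holds overall, its expected value is 33.33 × [1 − (S − 1)/149]. The loss is 150 × (S − 1)/149, or about S − 1 patients. For S = 8: 33.33 × 142/149 = 31.77; 0.5 × √31.77 = 2.82; df 150 − 8 − 1 = 141; power 79.9%.

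| Surgeons | Information kept, list ignores surgeon | Power, list ignores surgeon | Power, 2:1 blocks within surgeon | Gain (points) |
|---|---|---|---|---|
| 8 | 95.3% | 79.9% | 81.7% | 1.8 |
| 10 | 94.0% | 79.4% | 81.6% | 2.2 |
| 16 | 89.9% | 77.6% | 81.3% | 3.7 |
| 24 | 84.6% | 75.0% | 80.5% | 5.5 |

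The third column is from the formula; simulated allocations agree within about 0.2 points. The fourth is simulated. The small loss left there comes from unfinished blocks and depends on how evenly surgeons enrol: with equal numbers per surgeon and blocks of 3, the 24-surgeon figure is 81.5%.

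By the t calculation, power passes below 80% between 7 surgeons (80.2%) and 8 (79.9%). By the normal approximation, 8 surgeons give 80.5% and 10 give 79.9%.

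**4. If lists are already blocked 2:1 by site** (block size 3 assumed, 8 sites, simulated): one surgeon per site gives 81.7%, the same as blocking by surgeon; two per site, 79.4%; three per site, 76.9%.

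**5. If 1000 mL is the total SD.** When surgeons explain a share r of the variance, adjustment removes it and information is divided by 1 − r. Power with a list that ignores surgeon:

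| Surgeons | r = 2% | r = 5% | r = 10% |
|---|---|---|---|
| 8 | 80.7% | 81.9% | 83.9% |
| 16 | 78.4% | 79.6% | 81.7% |
| 24 | 75.8% | 77.1% | 79.3% |

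At r = 5%, blocking within surgeon gives 83.6%, 83.4% and 82.8%. The gain from blocking (1.7, 3.8 and 5.7 points) is about the same as in step 3.

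**6. Surgeons with one arm only.** The chance that n patients all fall in one arm is (2/3)^n + (1/3)^n: 9/27 = 33% for 3 patients and 17/81 = 21% for 4. With equal enrolment, the expected number of surgeons with active patients only is 8 × (2/3)^18.75 = 0.004, 16 × (2/3)^9.375 = 0.36 and 24 × (2/3)^6.25 = 1.9.

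**The case against.** The strongest reply is that this is a reporting gap and not a shown loss of power. The only count in the documents is 8 sites. With one surgeon each, power is 79.9% or 80.5% according to the approximation, which is the target within rounding. A schedule keyed to site-prefixed numbers is naturally read as one list per site; if those lists are in 2:1 blocks with one surgeon per site, nothing is lost. Section 11.2 attributes the SD to the restricted surgery type and population, which reads more like a total SD, and then adjustment gives back part or all of the cost. All of this stands, and it makes the size conditional.

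A reader might also infer three stronger things that the documents do not support:

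- **Whole strata of the binary analyses will be lost.** With about 19 patients per surgeon this is very unlikely (step 6); it matters only with many small surgeons. Section 11.4.3 makes the Cochran-Mantel-Haenszel test a fallback for low incidences and does not name its strata.
- **Nothing can be done at analysis.** Prespecified pooling of small surgeons, or a random surgeon effect, would recover part of the loss.
- **Blinded kits remove any predictability.** Section 8.4 supplies an emergency decoding unit for each kit. In a 2:1 block of 3, decoding one placebo kit reveals that the other two are active.

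The objection does not remove the mismatch between allocation and model. No text provides for blocking, site is not surgeon, and Site 6 lists more than one investigator.

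**Conclusion.** The point holds in conditional form. The plan adjusts for surgeon without providing for balance by surgeon. If the list ignores surgeon, the expected cost is about S − 1 patients' information: about 7 patients and 1.8 points of power at 8 surgeons, 15 patients and 3.7 points at 16, 23 patients and 5.5 points at 24.

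A reader might infer that power is below 80% even with no losses. The documents do not establish that. It requires roughly 8 to 10 or more surgeons, a list not already blocked by site with one surgeon each, and 1000 mL as the within-surgeon SD. Nor is there bias or inflation of type I error, since adjusting for a factor that was not stratified is valid.

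What makes a modest loss visible is the thin margin of 6 patients in step 2, which arises because the 128 in section 11.2 is an equal-group figure applied to a 2:1 trial. That is a separate and larger matter.

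Blocking 2:1 within the factor the model already uses costs no precision on any reading and gains some on most, so the change is worth making as an inexpensive improvement.

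**What to change.** In section 8.4, state that the schedule, or the part not yet used, is stratified by surgeon, with surgeons expected to enrol few patients pooled within site, and uses permuted 2:1 blocks of varying size. Keep the block sizes in a restricted randomisation document and out of the protocol that investigators read. In section 11.4.2, define the surgeon factor with the same pooling. Give the expected number of surgeons per site, and say in section 11.2 whether 1000 mL is the total or the within-surgeon SD. If lists blocked by site already exist, say so; with one surgeon per site no further change to the list is needed.

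Cost: regenerating the unused list, more kit logistics at the site pharmacies with possibly spare kits per stratum, and a small predictability risk if a kit is decoded in an emergency, which varying and undisclosed block sizes reduce.

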9. STUDY AGENT

9.1. Study Agent(s) Administration

9.1.1. Study Agent(s) Description

Test Drug: Exela's Tranexamic Acid Intravenous Infusion Bags (10 mg/mL), manufactured and provided by Exela Pharma Sciences, LLC from a single batch / lot will be administered to all randomized subjects.

Test Placebo: Inactive ingredient mixture for injection without drug, intravenous infusion bags containing normal saline, manufactured and provided by Exela Pharma Sciences, LLC from a single batch / lot will be administered to all randomized subjects.

9.1.2. Dosing and Administration

Infuse 3 mL/kg over one hour followed by continuous infusion at 0.3 mL/kg for maximum infusion volume of 5 mL/kg.

9.1.3. Formulation, Appearance, Packaging, and Labeling

The trial drugs will be supplied as kits containing seven (7) identically appearing intravenous bags containing 100 mL of an intravenous solution. Each bag will have a label affixed to it which states the kit-number, bag-number, and directions. A single kit will be used for each subject and will contain tranexamic acid infusion bags or saline bags. *[The number of bags per kit can be changed depending on the longest anticipated surgery time and/or the anticipated highest subject weight]*

9.2. Preparation/Handling/Storage/Accountability

9.2.1. Acquisition and Accountability

The Principal Investigator will maintain accurate records of receipt of all test articles, including dates of receipt. In addition, accurate records will be kept regarding when and how much of each test article is dispensed to and used by each individual subject in the study. Reasons for deviation from the expected dispensing regimen must also be recorded. A Drug Dispensing Form will be provided for this purpose and will be signed by the Principal Investigator at the conclusion of the study.

9.2.2. Product Storage and Stability

Tranexamic Acid Injection (10 mg/mL) should be stored at controlled room temperature (20 – 25 °C; or 68 – 77 °F). Under these conditions Tranexamic Acid Injection (10 mg/mL) is stable for 2 years from date of manufacture.

9.2.3. Preparation

Tranexamic Acid Injection (10 mg/mL) is suitable for direct administration and no additional preparation is necessary.

9.2.4. Retention Samples

Retention (reserve) samples of the test formulations will be selected and retained by the Principal Investigator (or Investigational Pharmacist) in a locked, secure pharmacy cabinet in compliance with the individual clinical site SOP requirements.

The retention period is to be at least five years following the date on which a full or abbreviated NDA or supplemental application is approved, or if not approved, at least five years following the completion of a bioavailability/bioequivalence study. To ensure compliance, Exela/SpineMark will conduct a yearly audit. The drugs will be stored under specified conditions in a designated storage area, locked and with limited access. The investigator will be informed by

Exela/SpineMark at the appropriate time when and how to return the retention samples.

10. STUDY PROCEDURES AND SCHEDULE

10.1. Study Procedures/Evaluations

10.1.1. Study Specific Procedures

Vital Signs Assessments

Vital signs will be monitored just prior to and during surgery and any abnormal vital signs result that is considered clinically significant by the Investigator will be recorded as an adverse event.

Physical Examination

A full physical examination will be performed at the screening visit and prior to discharge from the study or at early termination. A full physical examination includes assessment of general appearance and evaluation of dermatological system, head, eyes, ears/nose/throat, neck, lymph nodes, lungs, heart, abdomen, neurological, and musculoskeletal system.

10.2. Laboratory Procedures/Evaluations

10.2.1. Clinical Laboratory Evaluations

Hematology, chemistry including metabolic profile and urinalysis evaluations will be performed at the pre-operative screening visit and prior to discharge from the study. An abnormal clinical laboratory test result that is considered clinically significant by the Investigator will be recorded as an adverse event and follow-up clinical laboratory evaluations may be performed at the discretion of the Investigator.

Hemoglobin content of the collected blood samples will be done by the clinic site or an accredited lab. Hematocrit concentration of the collected blood samples will also be determined.

Clinical chemistry assessments will be done by the clinic site or an accredited lab.

10.2.2. Other Assays or Procedures

No other assays or procedures are planned for this study

10.2.3. Specimen Preparation, Handling, and Storage

Blood samples for hemoglobin measurement will be collected prior to start of procedure, at the end of the procedure, at 24 h, and every 24 h thereafter until discharge. Hematocrit analysis will also be conducted on all collected blood samples.

Blood lost during surgery will be collected by subfascial Hemovac drains at the incision site into canisters containing heparinized saline. Volumes collected will be recorded post-surgery and every 24 h thereafter until discharge and removal of the two subfascial drains.

10.2.4. Specimen Shipment

Each clinical site will have established procedures for sample shipment as necessary.

10.3. Study Schedule

10.3.1. Screening

Prior to surgery, subjects will provide written informed consent and will then undergo pre-operative data collection/screening, including:

- Inclusion Exclusion criteria assessment
- Diagnosis leading to surgery
- Planned procedure

-
- Schwab Curve type and coronal curve magnitude (Cobb angle)
 - Patient age and demography
 - Height, Weight, and Body Mass Index
 - Number of units of autologous blood donation
 - CBC: Hb/Hct/WBC/platelet count (post-autologous donation)
 - Coagulation Profile: PT/PTT/INR
 - Medical History and Medication Use
 - History of Previous Spine Surgery
 - Drug / Alcohol / Tobacco Use
 - Medication Allergies
 - Pregnancy testing (females only)

10.3.2. Pre-Treatment Procedures

A urine pregnancy test will be performed (females only).

10.3.3. Drug Dosing

Blinded treatments will be administered at an initial dose of 3 mL/kg as a one hour infusion using a calibrated infusion pump prior to start of procedure, and as a 0.3 mL/kg/h infusion during surgery up to a maximum infusion volume of 5 mL/kg. Each treatment will be administered by a calibrated infusion pump. The pump's manufacturer, model, and serial number will be recorded on the CRF. The volume infused remains constant regardless of whether the patient is receiving tranexamic acid or saline.

At the termination of the trial, all unused trial medication must be returned to Exela Pharma Sciences. Instructions for the return of trial medication will be provided by Exela at the completion of the trial.

Blood samples for hemoglobin measurement will be collected prior to start of procedure, at the end of the procedure, at 24 h, and every 24 h thereafter until discharge. Hematocrit analysis will also be conducted on all collected blood samples.

The following data will also be recorded:

- Treatment ID
- Details of surgical procedure [Number of vertebrae fused, number of anchors used, and type of anchors used (screws, hooks, or anchors); Number and type of osteotomies performed]
- Any complication prolonging the surgery time or increasing patient blood loss
- Surgery time
- Estimated blood loss peri-operatively (from drainages and absorbent/surgical pads)
- Volume of cell saver delivered
- Units of autologous transfusion and allogenic transfusion
- Units of fresh frozen plasma and platelets administered
- Volume of crystalloids/colloids given
- Urine output
- Location of Hemovac drains and number of drains placed
- Drain output recorded daily
- Length of drain use (uniformly remove drains when output <120 mL/day)
- Length of hospital stay
- Complications of autologous or allogenic transfusion
- Complications of tranexamic acid including renal, hepatic, thromboembolic, and brain/CNS
- Functional recovery assessments will be completed prior to discharge
- Any wound complications for the duration of hospitalization

10.3.4. Follow-Up Procedures

Follow-ups on wound complications and on adverse events related to tranexamic acid (such as seizures, DVTs, and PEs) will be conducted minimally every 24 h during hospital stay and at 6 weeks.

Adverse events (AEs) will also be monitored by the investigator and/or designated research staff and spontaneous reporting throughout the study.

